7.11 Remote monitoring and management system of haemodynamic data

The CardioMEMS™ Heart Failure System (27) provides pulmonary artery hemodynamic data used for monitoring and management of Heart Failure patients. The system includes an implantable wireless sensor with delivery catheter, a remote monitoring electronics system, and a System database.

The wireless sensor is implanted into the distal pulmonary artery. Once implanted, the CardioMEMS Pulmonary Artery Sensor provides non-invasive hemodynamic data that is collected in the System database. The dataset includes details on the pulmonary artery pressure waveform, systolic, diastolic, and mean pulmonary artery pressure and cardia rhythm (heart rate). This hemodynamic data is transferred online to a secure website that serves as the System database, so that monitoring information is available at all times.

7.12 Implementation of measures against Covid-19

This study is conducted in accordance with Covid-19 Guidance from Public Health England and Public Health Scotland, Infection Prevention and Control (IPC) Recommendations, and local implementations of all involved NHS partner sites as well as the affiliated laboratories and clinical facilities where this study shall take place. Local rules and recommendations apply to all study participants and all clinical and non-clinical personnel involved for the conduct of the study in the UK. The above should read in conjunction with current NICE Covid-19 guidelines and relevant regulations and standard operating procedures. Recommendations are not mandatory and allow for local modification and adaptation.

8. PHARMACOVIGILANCE

For full details including grading of Adverse Events, please refer to Appendix 2 - NCI Common Terminology Criteria for Adverse Events adapted for PIPAH study.

8.1 Definitions

Adverse Event (AE): Any untoward medical occurrence in a patient or clinical trial subject administered a medicinal product and which does not necessarily have a causal relationship with this treatment. *An AE can therefore be any unfavourable and unintended sign (including an abnormal laboratory finding), symptom, or disease temporally associated with the use of an IMP, whether or not considered related to the IMP.*

Adverse Reaction (AR): All untoward and unintended responses to an IMP related to any dose administered. All AEs judged by either the reporting Investigator or the Sponsor as having reasonable causal relationship to a medicinal product qualify as ARs. The expression reasonable causal relationship means to convey in general that there is evidence or argument to suggest a causal relationship.

PIPAH Study Page 34 of 47

Unexpected Adverse Reaction: An AR, the nature or severity of which is not consistent with the applicable product information [e.g. Investigator's Brochure for an unapproved investigational product or summary of product characteristics for an authorised product]. When the outcome of the AR is not consistent with the applicable product information this AR should be considered as unexpected. Side effects documented in the summary of product characteristics which occur in a more severe form than anticipated are also considered to be unexpected.

Serious Adverse Event (SAE) or **Serious Adverse Reaction (SAR):** Any untoward medical occurrence or effect that at any dose:

- results in death
- **is life-threatening -** refers to an event in which the subject was at risk of death at the time of the event; it does not refer to an event which hypothetically might have caused death if it were more severe.
- requires hospitalisation, or prolongation of existing inpatients' hospitalisation
- · results in persistent or significant disability or incapacity
- is a congenital anomaly or a defect

Medical judgement should be exercised in deciding whether an AE/AR is serious in other situations. Important AE/ARs that are not immediately life-threatening OR do not result in death or hospitalisation but may jeopardise the subject or may require intervention to prevent one of the other outcomes listed in the definition above, should also be considered serious.

Suspected Unexpected Serious Adverse Reaction (SUSAR): Any suspected AR related to an IMP that is both unexpected and serious.

8.2 Assigning causality

Each AE must be assessed by the site Investigator as to whether or not there is a reasonable possibility of a causal relationship to the study drug. The assignment of the causality should be made by the site Investigator responsible for the care of the participant using the definitions below. If any doubt about the causality exists the site Investigator should inform the study coordination centre who will notify the Chief Investigator.

In the case of discrepant views on causality between the site Investigator, Chief Investigator and others, all parties will discuss the case. In the event that no agreement is made, the Medicines and Healthcare Products Regulatory Agency (MHRA) will be informed of both points of view.

8.2.1 Causality description

Most AEs and drug ARs that occur in this study, whether they are serious or not, will be expected treatment-related toxicities due to the drugs used in this study. The assignment of the causality should be made by the site Investigator responsible for the care of the participant using the definitions in the table below.

Relationship	Description
Unrelated	There is no evidence of any causal relationship
Unlikely	There is little evidence to suggest there is a causal relationship (e.g. the event did not occur within a reasonable time after administration of the trial medication). There is another reasonable explanation for the event (e.g. the participant's clinical condition, other concomitant treatment).
Possible	There is some evidence to suggest a causal relationship (e.g. because the event occurs within a reasonable time after administration of the trial medication). However, the

PIPAH Study Protocol Version 5.0, 19-MAY-2022

	influence of other factors may have contributed to the event (e.g. the participant's clinical condition, other concomitant treatments).
Probable	There is evidence to suggest a causal relationship and the influence of other factors is unlikely.
Definitely	There is clear evidence to suggest a causal relationship and other possible contributing factors can be ruled out.
Not assessable	There is insufficient or incomplete evidence to make a clinical judgement of the causal relationship.

8.3 Assigning severity

For each AE, intensity should be defined according to the following criteria:

Mild	Awareness of sign or symptom, but easily tolerated
Moderate	Discomfort enough to cause interference with normal daily activities
Severe	Inability to perform normal daily activities
Life threatening or disabling	Immediate risk of death from the reaction as it occurred
Death	The event resulted in death

8.4 AE reporting procedures

8.4.1 Screening period

SAEs occurring between signing the informed consent form and study drug initiation are only required to be reported if they are considered by the site Investigator to be related to study-mandated procedures.

8.4.2 Treatment period

All AEs should be reported. Depending on the nature of the event the reporting procedures below should be followed. Any questions concerning AE reporting should be directed to the study coordination centre in the first instance.

8.4.2.1 Non serious AR/AEs

All such toxicities, whether expected or not, should be recorded in the AEs section of the CRF.

8.4.2.2 Serious AR/AEs

All SAEs must be reported to the study coordination centre within 24 hours of the site Investigator being made aware of the event. The site Investigator should complete the SAE form and send it to the study coordination centre together with relevant treatment forms and anonymised copies of all relevant investigations. Follow-up information about a previously reported SAE must be reported within 24 hours of receiving it.

However, relapse and death due to pulmonary hypertension, and hospitalisations for elective treatment of a pre-existing condition do not need reporting as SAEs.

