An interim analysis is planned after 13 patients have completed the 24 week treatment on the highest tolerated dose. If there are 1 or no responses in these patients, the study will be stopped. Otherwise, additional patients will be recruited for a total of 34 evaluable patients. The null hypothesis will be rejected if 7 or more responses are observed in the 34 patient cohort. Blood levels of Imatinib will be measured in each patient at baseline and at the end of Weeks 4 and 24. A trough level (noting the time for last dose) will be measured at the assessment on Week 4 and that on Week 24. Dose-limiting toxicity is defined as discontinuation of treatment for more than 5 consecutive days due to Grade 2 or above Adverse Events defined by the NCI Common Terminology Criteria for Adverse Events (version 5.0, 2017), adapted for this study - see Appendix 2. The criteria have been adapted by removing reference to pulmonary hypertension as an adverse event (since this is the indication for this study).

The most common recognised side effects of Imatinib include:

- Muscle cramps
- Joint pains
- Nausea and vomiting
- Swelling of the ankles and face
- Skin rash
- Loose stools
- Unusual bleeding or bruising
- Fatigue

Leg oedema and weight gain can also indicate deterioration in PAH due to right heart failure, rather than Imatinib toxicity. At the discretion of the study physician, a trial of increased dose of diuretics is permitted to help reduce the oedema and weight gain. If the oedema and weight gain are judged to be due to Imatinib toxicity, the dose of Imatinib may be reduced or the drug stopped and the patient is managed according to best clinical practice.

If a patient is unable to continue with the prescribed dose of Imatinib to 24 weeks, they will be withdrawn from the study. These patients may continue with a lower dose of Imatinib or discontinue the drug under the guidance of their local NHS specialist physician.

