4.2 Discussion of study design

The first part of this study is open label, single dose escalation. The aim is to find a safe dose that is tolerated in the target patient population. Doses will be escalated at intervals between patients, guided by a statistical model and an independent Data Monitoring Committee. The starting and maximum doses (i.e. dose range) to be investigated is based on a Phase 3 study [IMPRES (10)] and clinical experience. Our planned sample size, as is generally the case for Phase I trials, is dictated by practical constraints, even more so when the condition being treated is rare (as is PAH). However, simulation studies of the most likely scenario based on the IMPRES trial (10) and expert opinion have shown that a sample size of 13 resulted in a 90% chance of recommending a dose with an associated toxicity within 10% of the target toxicity level (20%) in the most likely scenario. We will be updating the skeleton graph -see Section 10- and revising the number of patients required overall after each patient is treated. We will also consider criteria for extending the sample size if needed and feasible.

The recruitment rate is dictated by the time to assess safety and tolerability at each dose. The decision to escalate dose, identify the highest tolerated dose, and Go/No-Go decision for Part 2 will be made by the independent Trial Safety and Data Monitoring Committees, comprising of lead clinician(s), and oncologist with expertise in the use of Imatinib and a Senior Trial Statistician.

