7.10 Right heart catheterisation (RHC)

RHC will be conducted at screening (Visit 1) and at the end of Week 24 in patients who do not have an implanted CardioMEMS™ device. The RHC at baseline can be omitted as long as the patient had one within a

^{*}for women of childbearing potential

month prior to screening for reasons not related to the study (e.g. for clinical purposes). On this occasion, retrospective RHC data (up to one month old) can be used for both the screening and baseline RHC entries. A qualified physician will be responsible for interpreting the RHC results. Any RHC finding that is judged by the site investigator as a clinically significant change (worsening) will be considered an Adverse Event. In a RHC procedure the catheter passes through the veins to the right side of the heart. Fluoroscopic X-ray images are used to guide the tip of the catheter up to the heart. A special type of dye called contrast medium is injected through the catheter and X-ray images (angiograms) are taken. The contrast medium is visible on the angiograms, showing the blood vessels that the contrast travels through and clearly highlights any blood vessels that are narrowed or blocked.

The amount of radiation used during the procedure depends on the complexity of the procedure but is approximately equivalent to about 7mSv effective dose, which is equivalent to about 3 years of natural background radiation. The maximum total radiation dose from the CT head scan (see above) and RHC procedures involved in this study is about 16 mSv. This is equivalent to approximately 7 years of natural background (2.3mSv/year) radiation. The risk of developing cancer as a consequence of taking part in this study is about 0.08 % (1 in 1250), which is low. For comparison, the natural lifetime cancer incidence in the general population is about 50%.

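### Relapse and death due to pulmonary hypertension are exempt from SAE reporting with no substitute route, so the committees deciding dose and Go/No-Go could miss them

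*Protocol*

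**What the plan says.** Section 8.1 of the protocol lists the outcomes that make an event serious. The first is that it "results in death"; another is that it requires hospitalisation. Section 8.4.2.2 requires SAEs to reach the study coordination centre within 24 hours, but adds that "relapse and death due to pulmonary hypertension, and hospitalisations for elective treatment of a pre-existing condition do not need reporting as SAEs". Section 8.4.2 states the general rule for the treatment period: "All AEs should be reported".

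Section 4.1 defines the Part 1 dose-limiting toxicity (DLT) as "discontinuation of treatment for more than 5 consecutive days due to Grade 2 or above Adverse Events defined by the NCI" criteria, as adapted in Appendix 2. On the adaptation it says: "The criteria have been adapted by removing reference to pulmonary hypertension as an adverse event". It also says: "Leg oedema and weight gain can also indicate deterioration in PAH due to right heart failure, rather than Imatinib toxicity".

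On who acts on these data, Section 4.2 gives the role to independent committees for safety and for data monitoring: "The decision to escalate dose, identify the highest tolerated dose, and Go/No-Go decision for Part 2 will be made by the independent Trial Safety". Section 10 promises SAE counts from Part 1. Section 11.6 lists serious emerging adverse events with an unacceptable risk/benefit ratio among the grounds for halting recruitment.

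**The concern.** The exemption depends on one judgement: that the relapse or death was due to pulmonary hypertension. The site makes that judgement knowing the treatment and without a control group. The protocol itself says that some signs of the disease and of the drug overlap. If the label is wrong, the text does not ensure that anyone else looks at the case.

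Two things are at stake. The first is patient safety. Section 8.1 treats an event as an adverse reaction if either the investigator or the sponsor sees a reasonable causal link, and the sponsor can form that view only on cases that reach it. The second is the dose decision. The committees choose the dose that goes into Part 2, and the safety data they rely on could leave out serious events of uncertain cause.

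**Working it through.** No stated figure is in dispute, so the main check compares the provisions.

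**1. Does another rule bring the exempt events back?**

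- *Seriousness (8.1).* A death from pulmonary hypertension is serious. An unplanned PAH admission is serious too. Because relapse is undefined, it is unclear whether such an admission is exempt.
- *CRF recording (8.4.2.1).* This procedure covers non-serious events. A PH-attributed death is serious, so it falls under 8.4.2.2, which exempts it and names no other form or deadline.
- *Reporting to the sponsor (8.6).* A footnote to the reporting overview excepts events that the protocol identifies as not needing immediate reporting, which appears to carry the exemption forward.
- *General AE rule (8.4.2).* It still applies, but sets no deadline and does not require notice to a committee.
- *Causality (8.2).* A site in doubt should inform the coordination centre. This depends on the site having doubt.
- *Test-based findings (7.8, 7.10).* Worsening on ECG or echocardiogram is an adverse event. For catheterisation the rule reads: "Any RHC finding that is judged by the site investigator as a clinically significant change (worsening) will be considered an Adverse Event". Catheterisation is scheduled only at entry and Week 24.
- *Remote data (4.1).* These can go to the committees on request, and only for patients with implanted monitors.
- *Outcome measures (3.1 to 3.3).* Death, relapse and clinical worsening are not among them.

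None of these requires a PH-attributed death or relapse to reach the committees promptly.

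**2. Could such an event also escape the DLT count?**

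The DLT needs a Grade 2 or higher event in the adapted criteria. Only reference to pulmonary hypertension is said to have been removed. Whether right heart failure, oedema or weight gain remain as gradable terms depends on Appendix 2. The answer is therefore possibly, not certainly.

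**3. How often might a death fall in the escalation window?**

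Inputs: 58% five-year mortality (Section 1.1, idiopathic/heritable PAH); a 4-week window; at most 13 patients in Part 1 (Section 10). Assumption: constant hazard.

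- Hazard = −ln(1 − 0.58)/5 = 0.1735 per year.
- 4-week risk = 1 − exp(−0.1735 × 4/52.18) = 1.3%.
- Expected deaths in 13 patients = 13 × 0.0132 = 0.17.

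**4. If one event were left out of the DLT count, would the dose move?**

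Figure 6 is not shown, so this is an illustration only. A one-parameter power model with a 20% target was run under three assumed skeletons, each with 20% at 200 mg: (0.10, 0.20, 0.30, 0.40), (0.05, 0.20, 0.35, 0.50) and (0.12, 0.20, 0.28, 0.36). Prior SDs were 1.16 and 0.75, giving six settings.

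| Patients so far | Events counted | Model dose | With one event omitted |
|---|---|---|---|
| 1 at 100 mg, 2 at 200 mg | 1 | 100 mg in all six | 300 or 400 mg in all six (the 100 mg step limits this to 300 mg) |
| 1 at 100 mg, 5 at 200 mg | 2 | 100 mg in all six | 200 mg in all six |
| 1 at 100 mg, 8 at 200 mg, 4 at 300 mg | 3 | 200 mg in all six | 300 mg in three, 200 mg in three |
| 1 at 100 mg, 12 at 200 mg | 3 | 200 mg in four, 100 mg in two | 200 mg in all six |

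One uncounted event can change the assigned dose early in Part 1. At 13 patients it does so only in some settings.

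**The case against.** The strongest reply is that the protocol does not hide these events. A definition of seriousness followed by a reporting exception is not in itself a contradiction, and 8.6 anticipates such exceptions. All adverse events are still reportable, all SUSARs must still be notified (8.5), and 8.2 gives doubtful causality a route to the Chief Investigator and, if disagreement persists, to the regulator. In dose finding, patients enter one at a time, at least 4 weeks apart, with calls at Weeks 1 to 3 and an assessment at Week 4. A death in that window would be hard to overlook.

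Much of this stands for a death in Part 1 dose finding. It is weaker for non-fatal deterioration, which is less conspicuous and can be labelled as relapse. It does not carry over to the extension phase or Part 2, where patients may be enrolled in parallel. A committee charter might add a route, but none is shown and the protocol does not require one.

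Three stronger readings are tempting but not supported.

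- *A PH-attributed death is certain to enter the dose model as non-toxic.* The DLT definition does not require attribution to imatinib, only pulmonary hypertension is said to have been removed, and Appendix 2 is not shown.
- *Several hidden deaths should be expected during escalation.* The same hazard over 24 weeks gives about 7.7%, or 2.6 deaths in 34 patients, but that is the wrong window. The 58% also describes idiopathic/heritable disease, whereas the trial admits other PAH types and excludes patients with a PAH admission or therapy change in the previous 3 months. The protocol gives no split by cause of death.
- *Every early death or PAH admission should count as a DLT by default.* That would charge disease progression to the drug and could bias the selected dose downward.

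**Conclusion.** The concern holds as a gap in reporting. A death or deterioration attributed to pulmonary hypertension need not be reported as an SAE, and no other provision requires it to reach the coordination centre or the committees promptly. The SAE counts, the halting criteria and the decisions on escalation and Go/No-Go could therefore miss it. Whether it could also escape the DLT count depends on Appendix 2.

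The expected number of deaths in the 4-week window is small: about 0.17 in 13 patients, assuming a constant hazard and that the idiopathic/heritable mortality figure applies. The practical risk lies mainly in non-fatal deterioration, for which the documents give no rate. The model runs show that a single event can matter early in Part 1, but they rest on assumed skeletons and on the event going uncounted.

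This should be corrected: the safety benefit is plain and the change is small.

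**What to change.** Reconcile Sections 8.1, 8.4.2 and 8.4.2.2:

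- Limit the exemption in 8.4.2.2 to hospitalisations for elective treatment of a pre-existing condition.
- Report every death and every unplanned PAH-related admission as an SAE within 24 hours, whatever the attributed cause. The undefined term relapse then drops out of the reporting rule.
- Send each such case to the Data Monitoring Committee; in Part 1, before the next dose is assigned.
- State that the committee decides, case by case, whether the event counts as a DLT.

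The cost is a few additional SAE forms and the committee's time to review them. The statistical design and sample size do not change.

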8.5 Reporting to the Regulatory Authorities

The Sponsor has delegated the responsibility for notifying the MHRA and REC of all SUSARs occurring during the study to the Chief Investigator. All SAEs and SUSARs must be reported in accordance with local regulatory guidelines:

Life threatening SUSARs should be reported to the MHRA and REC no later than **7 days** after the Chief Investigator has first knowledge of the minimum criteria for expedited reporting. Further relevant information should be given within a further 8 days.

[figure not shown]
PIPAH Study Page 36 of 47

Non-fatal and non-life threatening SUSARs should be reported to the MHRA and REC no later than **15 days** after the Chief Investigator has first knowledge of the minimum criteria for expedited reporting. Further relevant information should be given as soon as possible. An annual safety report will be submitted on the anniversary of the Clinical Trial Application to the MHRA and REC.

8.6 Reporting to the Sponsor

All SAEs and SUSARs must be forwarded the Imperial College Joint Research Office within 24 hours of the site Investigator learning of its occurrence.

Safety Reporting Overview

^{*} Unless identified in the protocol as not requiring immediate reporting

Contact details for reporting SAEs and SUSARs

[contact]

Chief Investigator: [contact]

Fax: not applicable Attention to: [name] / [name]

Please send SAE forms to: [contact] cc'ing [contact]

[contact] (Mon to Fri 09.00 – 17.00)

